# Document Type: Master Clinical Protocol 2018-10

# 1 LIST OF ABBREVIATIONS

Abbreviation	Definition
AA	Advanced Adenoma
AE	Adverse Event
CRC	Colorectal Cancer
CRF	Case Report Form
CUC	Chronic Ulcerative Colitis
DNA	Deoxyribonucleic Acid
EC	Ethics Committee
FAP	Familial Adenomatous Polyposis
FDA	Food and Drug Administration
FIT	Fecal Immunochemical Test
FoBT	Fecal Occult Blood Test
GCP	Good Clinical Practice
IBD	Inflammatory Bowel Disease
ICH	International Council for Harmonization
IRB	Institutional Review Board
IVD	In Vitro Diagnostic
HNPCC	Hereditary Non-Polyposis Colorectal Carcinoma (Lynch Syndrome)
MSTF	Multi Society Task Force
mt-sDNA	Multi-target stool DNA
SAE	Serious Adverse Event
UADE	Unanticipated Adverse Device Effect
USPSTF	United States Preventive Services Task Force

#### 3 PROTOCOL SYNOPSIS

Primary Objective: The primary objective is to confirm the specificity of the

multi-target stool DNA test (mt-sDNA), Coloquard, in an

average risk population, ages 45-49.

Study Design: Prospective, cross-sectional, multi-center study

Investigational Device Multi-target stool DNA test (mt-sDNA), Cologuard,

(Exact Sciences, Madison, WI)

Population: Subjects 45-49 years of age who are at average risk for

development of CRC. 914 subjects are targeted to

enroll.

Primary Endpoint: The primary endpoint of this study is specificity of the

mt-sDNA test (Cologuard) in the 45-49 age group in an

average risk population, using colonoscopy with histopathology (when required) as the reference method. The primary analysis requires the one-sided 97.5% lower bound of the specificity of Coloquard to

exceed 85.0%.

Study Duration: Duration of study participation for each subject will be

approximately 60 days from enrollment into the study.

Study Procedures: Subjects providing written informed consent to

participate in the study will complete the mt-sDNA test (Cologuard) followed by a screening colonoscopy which should be completed within approximately 60 days of enrollment. Subjects may also choose to consent to 2018-10B and provide a blood sample at the time of

[figure not shown]
enrollment.

#### 4 BACKGROUND / RATIONALE

#### 4.1 Background

The 2018 American Cancer Society colorectal cancer (CRC) screening guideline [1] now recommends initiating colorectal cancer (CRC) screening at age 45 in asymptomatic, average risk individuals. This change in a prominent national guideline was based on recent data [2] showing that the incidence of CRC in the 40-49 age group has increased with that of the 45-49-year-old group similar to that of 50-54-year-olds. There has been a 51% increase in the incidence of CRC from 1994 to 2014 and an 11% increase in mortality from 2005 to 2015 among individuals 55 years old and younger. Importantly, this change appears to be a birth cohort effect, likely starting for those born in the early 1950s who will carry this increased risk forward for their lifetimes. Compared to birth cohorts between 1890-1950 where the rate of CRC has been steadily declining, the rate in those generations born after 1950 has been steadily increasing. The ACS estimates that in 2014, over 7,073 cases of CRC were diagnosed in individuals aged 45 to 49 years with over 16,450 cases diagnosed in patients under 50.

Rising incidence of CRC in 40-49-year-olds compared to decreasing incidence in those 50 years of age and older (from Siegel R et al JNCI 2017 [2]).

Previously, a recommendation for starting at age 45 in average risk individuals was proposed by the 2009 American College of Gastroenterology guideline in African Americans [3] and reiterated in the 2017 U.S. Multi-Society Task Force CRC screening guideline [4]. The USMSTF includes members of the American Gastroenterological Association, the American College of Gastroenterology, and the American Society of Gastrointestinal Endoscopy. While the 2016 United States Preventive Services Task Force guideline did not recommend starting screening at age 45 [5] and continued to give its "A" rating to screening asymptomatic average risk individuals from ages 50-75, the data supporting a cohort effect generally showing increased risk in younger individuals were not available when the USPSTF reviewed the CRC screening evidence base prior to the 2016 guideline update.

According to [name], former Chair of the National Colorectal Cancer Roundtable and director of surgical oncology for the northwest region of Northwell Health, as quoted in the N.Y Times [6], "Solid epidemiological data from our national cancer registries documents a dramatic increase in the incidence of colon and especially rectal cancer among individuals under the age of 50, and the vast majority of those cases are in the 40- to 49-year-old age bracket."

Importantly, the ACS guideline includes the multi-target stool DNA test as one of the recommended methods for CRC screening, including for the expanded age range of 45-49 years of age. The ACS Guideline development group states, "The GDG concluded that mt-sDNA warrants inclusion among test options based on its sensitivity for detecting CRC, its improved advanced adenoma and serrated sessile polyp detection compared with FIT, and evidence indicating that some adults would choose screening

#### Master Clinical Protocol 2018-10

with mt-sDNA over other CRC screening tests."[7] Currently the labeled indication for mt-sDNA includes average risk asymptomatic individuals 50 years of age and older. In order to accommodate this change in medical practice, Exact Sciences wishes to expand the labeled indication for mt-sDNA into this 45-49 age group.

#### 4.2 Rationale

Given its high sensitivity for CRC and advanced pre-cancers demonstrated in the mt-sDNA pivotal study
[8],and given the safety of mt-sDNA as a non-invasive stool-based test, mt-sDNA could be an important
option for patients and providers in this younger age group.

The study is designed to provide additional evidence of test performance in this age group to support an application for FDA label expansion. Biologically, there is little reason to believe there is a significant difference in the underlying mechanism of CRC in average risk individuals age 45-49 vs. 50-59, which is included in the current label.

#### 5 OBJECTIVES

#### 5.1 Primary Objective

The primary objective is to confirm the specificity of the mt-sDNA test (Cologuard) in an average risk population, ages 45-49.

#### 6 ENDPOINTS

#### 6.1 Primary Endpoint

The primary endpoint of this study is specificity of the mt-sDNA test (Cologuard) in the 45-49 age group in an average risk population, using colonoscopy with histopathology (when required) as the reference method. The primary analysis requires the one-sided 97.5% lower bound of the specificity of Cologuard to exceed 85.0%.

#### 6.2 Other Outcomes

Other outcomes to be assessed include the following

- Sensitivity for CRC + advanced adenoma
- The positive and negative predictive values
- The positive and negative likelihood ratios (PLR and NLR, respectively)
- The distribution of colorectal epithelial lesions (by Category) among positive mt-sDNA test (Cologuard) subjects
- The rate of no mt-sDNA (Cologuard) result

#### Master Clinical Protocol 2018-10

#### 7 STUDY DESIGN

This is a prospective, cross-sectional, multi-center study to confirm the specificity of the mt-sDNA test (Cologuard) in average risk individuals ages 45 to 49.

All subjects enrolled into the study will be provided a stool collection kit for the mt-sDNA test (Cologuard) and scheduled for a screening colonoscopy. Stool sample collection must occur prior to subjects initiating bowel preparation for the colonoscopy procedure. All subjects will undergo a screening colonoscopy within approximately 60 days of enrollment.

The results of the mt-sDNA test (Cologuard) will be compared with the results of the colonoscopy and with any corresponding diagnostic histopathology results from biopsies or excised tissues obtained for clinical purposes to confirm the performance estimates.

Stool samples collected by the subject for the mt-sDNA test (Cologuard) will be sent to Exact Sciences Laboratories and tested. Individuals conducting the mt-sDNA tests will be blinded to all subject clinical information, including colonoscopy results. Investigators, subjects, and endoscopists will be blinded to the mt-sDNA test (Cologuard) results, and the results of the tests will not be used for clinical management of study subjects.

All subjects enrolled in the study will also be offered the opportunity to provide a blood sample for biomarker evaluation and assay optimization (Protocol 2018-10B). Blood samples will be used for research on biomarkers from plasma and serum.

#### 8 STUDY DEVICE

#### 8.1 Description of the Investigational Device

The mt-sDNA-based test (Cologuard) is a colorectal cancer screening option that consists of a stool collection kit and proprietary assay methodologies for the detection of fecal hemoglobin and fecal DNA markers known to be associated with CRC.

Cologuard is approved by the FDA for use in average risk adults ages 50 years or older. Cologuard has not been evaluated in average risk individuals under the age of 50.

The Stool Collection Kit includes: Sample Collection Instructions, a stool collection container and support bracket, a bottle of liquid sDNA preservative, a fecal hemoglobin sample tube, return shipping box, and return shipping label. The stool collection kits will be labeled as investigational use only. The stool collection kits will be provided by the Sponsor. The sites are responsible for management of the stool collection kits. The investigator must maintain complete and current accountability records (including kit receipt, dispensation, and return) for all kits supplied by the Sponsor. All unused kits and their original packaging should be kept on-site for reconciliation by a site monitor. The site must return all unused kits and packaging after accountability has been performed at the end of the study. Stool collection kit return must be documented in the accountability records.

#### 8.2 Regulatory History

Cologuard received Pre-Market Approval from the U.S. Food & Drug Administration on August 11, 2014 (P130017) (as well as approval for subsequent PMA supplements) with the following Indication for use:

Cologuard is intended for the qualitative detection of colorectal neoplasia associated DNA markers and for the presence of occult hemoglobin in human stool. A positive result may indicate the presence of CRC

# exact sciences

#### Document Type:

#### Master Clinical Protocol 2018-10

or AA and should be followed by diagnostic colonoscopy. Cologuard is indicated to screen adults of either sex, 50 years or older, who are at typical average-risk for CRC. Cologuard is not a replacement for diagnostic colonoscopy or surveillance colonoscopy in high risk individuals.

#### 9 SUBJECT SELECTION AND WITHDRAWAL

914 subjects are targeted to enroll. The following eligibility criteria are designed to select subjects who are at average risk for development of CRC. All relevant medical and non-medical conditions should be taken into consideration when deciding whether this protocol is suitable for a particular subject. No waivers to these criteria will be permitted.

#### 9.1 Inclusion Criteria

Subjects must meet the following criteria to be eligible for the study:

- 1. Subject is at average risk for development of CRC.
- 2. Subject is asymptomatic with respect to those symptoms that would ordinarily result in a colonoscopy to rule out CRC or clinical work-up for gastrointestinal pathology or disease.
- 3. Subject is 45-49 years of age at the time of enrollment through expected study completion, approximately 60 days after enrollment.
- 4. Subject is willing and able to sign informed consent.

#### 9.2 Exclusion Criteria

Subjects presenting with any of the following will not be included in the study:

- 1. Subject has a personal history of CRC.
- 2. Subject has ≥2 first-degree relatives who have been diagnosed with colon cancer.
- 3. Subject has a first degree relative with CRC diagnosed before the age of 60.
- 4. Subject has any of the following:
  - Overt rectal bleeding, e.g., hematochezia or melena (blood on toilet paper, after wiping, does not constitute rectal bleeding).
  - Unexplained iron deficiency anemia with a severity that would indicate a workup for gastrointestinal bleeding within the previous six (6) months.
  - Positive fecal occult blood test or FIT within the previous six (6) months.
  - Subject has had a previous colonoscopy.
- 5. Subject has a known syndromic hereditary condition (FAP, HNPC, etc.) or has a documented first degree relative with a known heritable cancer syndrome, including:
  - Familial adenomatous polyposis (also referred to as "FAP", including attenuated FAP and Gardner's syndrome). Hereditary non-polyposis CRC syndrome (also referred to as "HNPCC" or "Lynch Syndrome").
  - Other hereditary cancer syndromes including but are not limited to Peutz–Jeghers Syndrome, MYH-Associated Polyposis (MAP), Turcot's (or Crail's) Syndrome, Cowden's Syndrome, Juvenile Polyposis, Neurofibromatosis and Familial Hyperplastic Polyposis.
- 6. Subjects with Cronkhite-Canada Syndrome.
- 7. Subject has a diagnosis or personal history of inflammatory bowel disease (IBD) including chronic ulcerative colitis (CUC) and Crohn's disease.
- 8. Subject has a history of non-colorectal aerodigestive tract cancer.
- 9. Subject has had a prior colorectal resection for any reason other than sigmoid diverticular disease.
- 10. Subject has any condition that in the opinion of the investigator should preclude participation in the study.

# exact sciences

#### **Document Type:**

#### Master Clinical Protocol 2018-10

#### 9.3 Subject Withdrawal

Subjects may be withdrawn from the study by any of the following mechanisms:

- 1. Voluntary withdrawal of consent to participate by the subject at any time during the study.
- 2. Determination by the clinical investigator that it is in the best interest of the subject.
- 3. Determination by the Sponsor it is in the best interest of the subject or study.
- 4. Stool sample not provided within 30 days of enrollment.
- 5. Colonoscopy procedure is not done.

All data available from enrollment to subject withdrawal will be collected unless the subject withdraws consent from the study. Data for all study visits will be collected for subjects who discontinue participation but who do not withdraw consent. Withdrawal of consent must be documented by site personnel in the subject source record.

#### 9.4 Subject Replacement

Enrolled subjects may be replaced for any of the following reasons:

- 1. No stool sample provided and/or no completed colonoscopy procedure.
- 2. A valid stool sample result cannot be obtained for a subject after two (2) attempts (Section 10.4).

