#### 10.5 Sample Assays

Assay results will be recorded as 'Positive', 'Negative', 'Sample Could Not Be Processed', or 'No Result Obtained.' If there are no valid results, a repeat test may be requested. Repeat stool sample requests will be sent to the site. Repeat stool sample collection must occur prior to bowel preparation for the colonoscopy procedure. If a valid stool sample result cannot be obtained for a subject after two (2) attempts, the subject will be withdrawn and may be replaced.

The mt-sDNA test (Cologuard) result will not be provided to investigators for clinical management of study subjects. All mt-sDNA test results will remain blinded to investigators and study subjects.

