#### 10.6 Colonoscopy and Histopathology

Every subject will undergo a screening colonoscopy after completing a mt-sDNA test (Cologuard) test. Colonoscopies should occur as soon as possible following informed consent and stool collection. Subjects who have poor bowel preparation and will not repeat the procedure or subjects who do not complete a colonoscopy should be withdrawn and may be replaced. Bowel preparation procedures and colonoscopy will be performed following the usual practice at each clinical site. Personnel performing the colonoscopy and producing the resulting report and the personnel performing the histopathological review of tissue will remain blinded to the results of the mt-sDNA test (Cologuard) result.

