#### 10.8 End of Study

Subjects will be considered completed from the study when they have provided a stool sample and have completed their colonoscopy procedure, OR at the point of subject withdrawal per Section 9.3.

Ensure all data is assessed, entered into the CRF and reporting on AEs/SAEs, UADEs, and/or Protocol Deviations has occurred, if necessary.

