#### 16 A DEFINITION OF END TRIAL

End of Trial is defined when 731 subjects have completed required study procedures with complete data receipt or on the date of early termination notice.

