## 2 STATISTICAL AND ANALYTICAL PLANS

### 2.1 Study Parameters

- This prospective, cross-sectional, multi-center study will enroll subjects 45-49 years of age at average risk for development of colorectal cancer.
- Cologuard is intended for the qualitative detection of colorectal neoplasia-associated DNA markers and for the presence of occult hemoglobin in human stool.
- A positive Cologuard result may indicate the presence of colorectal cancer or advanced adenoma (AA) and should be followed by diagnostic colonoscopy; Cologuard is intended for adults of either sex, 50 years or older, who are typical average-risk candidates for colorectal cancer (CRC) screening.
- Subjects will be required to complete the mt-sDNA (Cologuard) test followed by a screening colonoscopy.
- Exact Sciences Laboratory will perform the Cologuard test.
- Cologuard results will be recorded as 'positive', 'negative', 'no result obtained' or 'sample could not be processed' for each individual corresponding to a specific stool sample.
- A valid mt-sDNA (Cologuard) test is defined as a result that is recorded as either 'positive' or 'negative.'
- A usable mt-sDNA (Cologuard) test is defined as a result that is recorded as either 'positive' or 'negative' (i.e. valid) and is received within 72 hours of sample collection.
- A colonoscopy must follow a Cologuard test.
- In the event of an additional colonoscopy due to inadequate preparation, the colonoscopy with the most significant findings will be considered the study colonoscopy and will be used as the reference test result in the analysis.
- A reportable colonoscopy is defined as one where the procedure was attempted, and a procedure report is available.
- A complete colonoscopy procedure will be considered and defined as: reaching the cecum (or) reaching the junction between the small and large intestine (in the event the cecum has been resected) or a colonoscopy wherein a CRC or AA was identified regardless of any limiting factors experienced during the colonoscopy.
- A subject is considered to be Per Protocol following a usable mt-sDNA (Cologuard) test and complete colonoscopy
- Subjects who have a colonoscopy following a Cologuard sample collection will be considered completed subjects and the date of completion will be the date that the last colonoscopy was performed.

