### 2.7.2 Subject Replacement Rules

Subjects who are withdrawn due to no stool sample provided within 30 days of enrollment or due to colonoscopy procedure not done may be replaced.

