### 2.9.2 Study Completion

Subjects who have a mt-sDNA (Cologuard) test and complete colonoscopy will be considered complete with respect to study procedure requirements. The date of study completion is the date of colonoscopy.

The study will end when all subjects have completed or discontinued including withdrawals.

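### Completion, replacement and end-of-trial rules do not tie the 731 to evaluable specificity cases, and no listed replacement ground covers a subject with one failed stool sample and no chance to repeat it

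*Protocol*

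**What the plan says.** **Completion.** Protocol 10.8: "Subjects will be considered completed from the study when they have provided a stool sample and have completed their colonoscopy procedure". SAP 2.1 is similar: "Subjects who have a colonoscopy following a Cologuard sample collection will be considered completed subjects". Neither asks for a positive or negative result. Appendix 2, footnote 4, asks only for the colonoscopy.

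**End of trial.** Protocol 16: "End of Trial is defined when 731 subjects have completed required study procedures with complete data receipt". The data-receipt condition is not defined. SAP 2.9.2 has a different rule: "The study will end when all subjects have completed or discontinued including withdrawals".

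**What 731 is elsewhere.** Table 1 in Protocol 12.3 gives it as the number of non-CRC/AA cases. Protocol 12.3.1 samples 731 colonoscopy negatives. SAP 2.2 sets it as the target for evaluable subjects with non-advanced neoplasia or negative findings, with enrollment capped at about 942.

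**Repeat samples.** Protocol 10.5: "Repeat stool sample collection must occur prior to bowel preparation for the colonoscopy procedure". Protocol 10.6: "Colonoscopies should occur as soon as possible following informed consent and stool collection".

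**Replacement.** Protocol 9.4 lists two grounds. The first is a missing stool sample or a colonoscopy not completed. The second is: "A valid stool sample result cannot be obtained for a subject after two (2) attempts (Section 10.4". (The two-attempt rule itself stands in 10.5, not 10.4.) SAP 2.7.2 is narrower: "Subjects who are withdrawn due to no stool sample provided within 30 days of enrollment or due to colonoscopy procedure not done may be replaced". It has no invalid-result ground, yet SAP 5 reports no change from the protocol's planned analysis.

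**Analysis.** Protocol 12.2 removes subjects without an evaluable test result from the primary analysis. SAP 2.8.1 removes them from the ITS and PP populations.

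**The concern.** The plan foresees that some stool samples will fail and that a repeat is possible only before bowel preparation. It has no rule for the remaining case: one failed sample, preparation already begun, colonoscopy done. That subject can be read as completed, falls under no listed replacement ground, and contributes nothing to specificity.

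This matters because Section 16 counts completed subjects, whereas the sample size justification counts evaluable category 3–6 subjects. The two counts also differ by the advanced neoplasia cases, who can complete every procedure but belong to sensitivity. If enrollment stops on the Section 16 count, the number available for the primary endpoint falls below 731. Protocol 12.3 raised the sample size from 225 to 731 for precision alone, so precision is what would be lost.

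**Working it through.** **Inputs.** Null 85.0%, alternative 92.2%, one-sided 2.5% exact test, n = 225 and 731, target interval 90.0% to 94.4%, drop-out 20%, enrollment 914 (all Protocol 12.3). Advanced adenoma prevalence 3.92% (Protocol 12.2). The rate of subjects with no valid result is not in the documents, so it is assumed: 2% as the main example, up to 10% as a stress case.

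**Step 1: follow one subject through the rules.** One sample is provided, the result is invalid, preparation has begun and the colonoscopy is completed.

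| Rule | Outcome |
|---|---|
| Protocol 10.8, SAP 2.1 | Completed |
| Protocol 9.4, ground 1 | Not met: sample and colonoscopy both exist |
| Protocol 9.4, ground 2 (also 10.5) | Not met: only one attempt was possible |
| SAP 2.7.2 | Not met: no invalid-result ground |
| Protocol 12.2, SAP 2.8.1 | Excluded from the primary analysis |
| Protocol 16 | Counted or not, depending on what the data-receipt condition means |

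**Step 2: reproduce the plan's figures.** Take the smallest r with P(X ≥ r | n, 0.85) ≤ 0.025; power is P(X ≥ r | n, 0.922).
- n = 225: r = 202, exact alpha 0.0237, power 92.6%. This is the smallest n from which power stays at or above 90%.
- n = 731: r = 641, exact alpha 0.0216, power 99.999%.
- Enrollment: 731 / 0.8 = 913.75, rounded up to 914.

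All three agree with the plan.

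**Step 3: precision.** The Clopper-Pearson lower limit is the 2.5% point of a Beta(x, n − x + 1) distribution, with x = 0.922n. At n = 731 it is 90.01%. It is still 90.00% at 724 and falls below 90.0% at 723. The margin is therefore 731 − 724 = 7 subjects.

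**Step 4: suppose 731 completers are counted instead of 731 evaluable cases.**
- 2% with no valid result: 731 × 0.02 ≈ 15, leaving 716.
- Advanced adenoma removed as well: 716 × (1 − 0.0392) ≈ 688.
- Stress case, 10% with no valid result: 731 − 73 = 658, then 658 × 0.9608 ≈ 632.

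| Evaluable n | Lower limit | Power |
|---|---|---|
| 731 | 90.01% | 99.999% |
| 724 | 90.00% | 99.999% |
| 716 | 89.99% | 99.999% |
| 688 | 89.94% | 99.998% |
| 632 | 89.83% | 99.995% |

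Upper limits run from 94.04% to 94.17%, inside 94.4%, so only the lower side binds. Observed counts are whole numbers, so real limits wobble by a few hundredths: 674/731 gives 90.02% and 634/688 gives 89.88%. The threshold of 724 is thus approximate. Of the 43 subjects lost between 731 and 688, about 15 come from invalid results and about 28 from advanced adenoma.

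**The case against.** Three stronger conclusions are tempting, and the documents do not support them.

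1. *The subject definitely counts toward the 731.* Section 16 adds the data-receipt condition, which could be taken to require a test result. Protocol 12.3 and SAP 2.2 define the 731 as evaluable cases, and SAP 2.9.2 runs the study until all subjects have completed or discontinued. The count is ambiguous, not settled against the plan.

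2. *The subject cannot be replaced.* Protocol 9.4 is a permissive list, not a prohibition. The study has a single arm, so replacing a subject only means enrolling another. The sponsor may also withdraw a subject in the study's interest (Protocol 9.3), although 9.4 does not list that as a replacement ground. Enrollment of 914 to about 942 leaves 183 to 211 subjects above 731 for losses of all kinds.

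3. *The trial would be underpowered.* It would not, even in the stress case. The success threshold is 85.0%, and 225 cases suffice for 90% power.

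It is also fair to say that many failed samples could be repeated in time. Stool is due within 30 days and colonoscopy within about 60, arriving kits are inspected, and sites are sent repeat requests. The no-result rate is a reported outcome, and excluded cases are to be assessed for bias.

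What stands after all this is that the documents attach two meanings to 731 and leave a foreseeable case without a rule. The enrollment allowance helps only if recruitment continues until 731 evaluable cases exist, and Section 16 does not say that it will.

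**Conclusion.** The text is wrong as written and needs reconciling, but the consequence is modest. Completion does not require a valid result, the primary analysis does, and the end-of-trial rule is worded in terms of the former. On the literal reading of Section 16, the trial can end with fewer than 731 evaluable category 3–6 subjects. Under the assumed 2% invalid rate and the plan's 3.92% prevalence, the lower limit at 92.2% is 0.06 percentage points under the stated 90.0%. The invalid rate is an assumption without support in the documents. The prevalence is the plan's own, and the larger part of the shortfall comes from it. The test of the primary hypothesis is unaffected.

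**What to change.** 1. In Protocol 16, define the 731 as category 3–6 subjects with a valid (positive or negative) mt-sDNA result and an evaluable colonoscopy, matching Protocol 12.3 and SAP 2.2. Either define the data-receipt condition or remove it. Align Protocol 10.8, SAP 2.1 and SAP 2.9.2 so that procedural completion by a subject is kept separate from that count.
2. In Protocol 9.4 and 10.5 and in SAP 2.7.2, allow replacement within the existing enrollment ceiling whenever no valid result exists, whatever the number of attempts. Correct the cross-reference in 9.4.
3. Reconcile the repeat-sample timing in Protocol 10.4 and 10.5 with the colonoscopy timing in 10.6. How that is scheduled is for the sponsor and sites to decide.

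The cost is wording in a few sections of both documents and possibly a few more subjects. The ceiling of about 942 holds if losses from all causes, including invalid results and advanced neoplasia, stay within 1 − 731/942 = 22.4%. If 2% invalid and 3.92% advanced adenoma came on top of a full 20% drop-out, 731 / (0.8 × 0.98 × 0.9608) ≈ 971 would be needed. The sponsor should therefore state what the 20% covers.
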